Most studies regarding language acquisition have focused on understanding when and how infants learn words. It is known that at 24 months, typically developing infants know and produce between 200 and 300 words (Jones & Smith, 2005; MacRoy-Higgins, Shafer, Fahey, & Kaden, 2016) and add to their vocabularies from 22 to 37 words each month (Vuksanovic & Bjekic, 2013). It is also during the first years of life that some principles that promote vocabulary learning are developed. The shape bias, which is a tendency to infer that objects that share the same shape will also share the same name, is the one that has been studied the most. At 24 months, typically developed infants present a shape bias and use it as a strategy to generalize words (Jones, 2003; Weismer, Venker, Evans, & Jones Moyle, 2013). In contrast, Late Talkers do not exhibit this preference and present a difficulty in organizing objects by shape (Jones, 2003). It has also been found that teaching typically developed infants a shape bias before the end of the second year of life boosts their vocabulary development (Smith, Jones, Landau, Gershkoff-Stowe, & Samuelson, 2002). Despite this, the possibility of teaching Late Talkers this principle and its effect on their vocabulary and language development has not been explored.

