3.3. Primary outcome measures

Objective A), i.e. whether children have learned a shape bias, will be assessed by means of a noun extension test with novel names and objects never heard and seen before by the infants at the end of the intervention programme.

Objective B), i.e. whether the intervention programme benefits infants' general vocabulary development, will be assessed with a vocabulary checklist filled in by the parents/guardians before and after both types of intervention. We will compare the vocabulary growth in the group of children that took part in the shape bias intervention programme with that of the group of children that took part in the 'specific word' intervention. A significant larger increase in the shape bias intervention compared to the 'specific word' intervention will provide information regarding the success or efficacy of the shape bias intervention.

Objective C), i.e. whether the shape bias intervention has a "long-term" effect on language development and cognitive abilities. Receptive and expressive language, and cognitive abilities, such as visual spatial skills and working memory, will be assessed at one year after the end of the intervention programme.

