4.2. Study design

Infants will be randomly allocated to one of two groups: shape training group or specific word training group. Over a series of 9 weekly sessions, all infants will be assessed on different tasks that can be divided into 5 stages: Vocabulary and developmental assessments, initial cognitive assessments, training sessions, first-order generalization test, higher-order generalization test. Depending on the group that the children will be in, they will receive either a shape training or a specific word training. Other assessments (initial assessments, cognitive assessments, first-order generalization test and higher-order generalization test) will be identical across the groups. Additionally, a follow up study will be conducted after one year of completion of the intervention programme. A table describing the intervention procedure is provided in Figure 1. Details of the tasks are given below.

[figure not shown]

Figure 1. Timeline of intervention programmes.

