4.3. Tests and procedure of intervention programme

4.3.1. Vocabulary and developmental assessments. At session 1, parents/guardians will fill in a socioeconomic and general development questionnaire (see Appendix 1.5). The

information provided in this questionnaire will double-check the inclusion/exclusion criteria. It will also be used to check whether the intervention was only successful in a sub-group of the infants (e.g. those without a family history of language problems). In the first and last session, parents/guardians will also be asked to fill in the UK-CDI Words and Gestures questionnaire, a vocabulary checklist of words and phrases that infants might know and use (Alcock, Meints, & Rowland, 2017; see Appendix 1.4). This will allow us to compare language development during the intervention programme between the two intervention groups.

4.3.2. Initial cognitive assessments: The initial cognitive assessments will be presented during the first two sessions. During week 1, infants will be assessed with a shape sorting task and an attention task. The sorting task will last no more than 5 minutes and will be used to assess if before the training programme, infants are sensitive to the shape of objects and can group objects by shape. Infants will be presented with 16 novel objects differing in shape, colour and texture and asked to sort them into groups. How to sort (namely by shape) will be shown to them with the means of examples. The attention task will last 3 minutes and will assess infants' joint and sustained attention. This will be achieved by monitoring their eye movements during the presentation of five short video clips (35 seconds each) of a person looking at and moving unusual novel objects. For this task, participants will sit on their parent/guardian's lap in front of a computer screen. Eye movement will be monitored with a remote eye tracker (see Figure 2). The parent will wear blacked-out glasses so that their behaviour cannot affect the infants' eye gazes.

At week 2, infants' visual spatial abilities and working memory will be assessed using the Wechsler Preschool & Primary Scale of Intelligence - Fourth UK Edition (WPPSI-IV UK). This test will last about 20 minutes and will be used to rule out any potential cognitive delay.

Figure 2. Attention task. Infants will watch five short videos and eye movements will be monitored with a remote eye tracker.

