6.3.2 Primary outcome analysis

During weeks 8 and 9 of the study infants will be assessed with two forced choice tasks where they will have to extend object names to new exemplars based on visual commonalities. We will assess the statistical difference between the response pattern and chance (using t-tests). This will show whether infants have learned to extend object names by shape similarities. The factors that predict the number of noun extensions based on shape as well as vocabulary growth will be assessed using mixed effect model analyses. The most important factors tested in the models will be the number of words known before the intervention, the intervention type (shape training vs specific word training), attention measures (pre-test and attention during training), and sorting task measure. The outcome of these analyses will show whether the shape bias intervention has led to a larger vocabulary growth than the specific word intervention (as a control intervention). It will also assess the role of attention in word learning and whether only infants that pay attention to novel items

presented to them or infants that are sensitive to shape similarities between objects can acquire a shape bias. Only data of infants that complete the intervention will be analysed.

Regarding the follow up study, infants' vocabulary and cognitive abilities will be assessed. This with the aim of analysing if there are any long-term effects of each intervention and infants continue learning words and potentially "catching up", or if the intervention programmes are only beneficial while they are being implemented. The cognitive assessments will be used to assess whether the intervention has an effect on visual spatial skills and working memory. In both cases, it will be done by comparing the infants results to the standardized mean of UK infant population. Similarly, infant's result in the follow up language assessment will be compared to the standarized mean of UK infant population.

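### The one-year follow-up analysis in 6.3.2 aims at the effect of each programme, but with two trained arms and only a UK norm as comparator it can support neither that nor Objective C's between-arm comparison

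*Combined protocol and SAP*

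**What the plan says.** Section 4.2 gives the design: "Infants will be randomly allocated to one of two groups: shape training group or specific word training group". Each group receives a training programme; there is no untreated or waiting group.

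For vocabulary over the programme, section 4.3.1 sets two measurements: "In the first and last session, parents/guardians will also be asked to fill in the UK-CDI Words and Gestures questionnaire". Section 3.3 ties success to a contrast between arms: "A significant larger increase in the shape bias intervention compared to the" specific word arm. Section 6.3.2 says the same of the mixed model, which is to show "whether the shape bias intervention has led to a larger vocabulary growth than the specific word intervention (as a control intervention"). Baseline vocabulary and intervention type are both named as model terms.

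The follow-up paragraph of 6.3.2 is worded differently. It looks for "any long-term effects of each intervention", with continued word learning and possible catch-up, or asks "if the intervention programmes are only beneficial while they are being implemented". The comparator it names, for the cognitive scores and for language alike, is the standardised mean of the UK population. It names no comparison between the two arms.

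Objective C in section 3.1 does promise one: language and cognition at one year, set against the specific word intervention.

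**The concern.** Both branches of the follow-up aim are absolute statements about each programme. The second takes benefit during the programme as given and leaves open only whether it lasts. Neither branch allows for the possibility that neither programme did anything.

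A design with two trained arms supports a relative statement: one programme did more, or less, than the other. It does not support a statement about either programme against no programme. If the arms do equally well or equally badly, nothing in the data separates both having worked, neither having worked, and ordinary development. The UK norm does not fill the gap, because a norm is not an untreated group of late talkers.

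At stake is what the one-year data will be used to say. As written, the plan leads towards conclusions the design cannot carry and omits the one randomised comparison that Objective C calls for.

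**Working it through.** **1. What the norm comparison estimates.** For arm k, write the mean gap from the UK norm at one year as

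G_k = D + C + R + H + E_k

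- D: the gap at entry. Children are selected for moderate or severe delay (section 4.1.1).
- C: spontaneous catch-up, which section 1.2 says occurs in some late talkers.
- R: regression to the mean after selection for delay.
- H: NHS intervention during the year. Section 4.1.3 says children with severe delay are invited to an NHS programme, with a wait of up to a year.
- E_k: the effect of programme k against no programme.

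An age-standardised norm allows for average growth with age. It does not remove D, C, R or H. One observed quantity per arm cannot identify E_k.

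For language the position is weaker still. The follow-up test is the BPVS3 (section 4.4), which is not given at baseline, while vocabulary during the programme is a parent checklist (section 4.3.1). A finding of benefit then but not now would compare two different instruments.

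**2. What a between-arm comparison estimates.** Under randomisation D, C and R are equal on average in the two arms, and access to H is the same, so in expectation

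G_shape − G_word = E_shape − E_word

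This is Objective C. It also shows the limit: if E_shape = E_word = e, the difference is 0 whether e is zero or large.

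**3. Why the nine-week analysis is not the problem.** "Over a series of 9 weekly sessions" puts 8 weeks between the first and last checklists: 56 / 30.44 = 1.84 months. The introduction says typically developing infants "add to their vocabularies from 22 to 37 words each month". That gives 22 × 1.84 = 40 to 37 × 1.84 = 68 words with no programme. The documents give no rate for late talkers. Assuming 25% to 75% of the typical rate gives 0.25 × 40.5 = 10 to 0.75 × 68.1 = 51 words.

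This growth is expected equally in both arms and cancels in the planned contrast, whose false-positive rate stays at the nominal 5%. It would matter only if growth were judged within an arm, which is not planned. For scale, take 12 children in an arm, no programme effect and a two-sided 5% one-sample t-test. The chance of a significant rise, by assumed SD of change (not in the documents), is:

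| SD of change | 20 words | 40 words | 68 words |
|---|---|---|---|
| 30 | 56% | 99% | about 100% |
| 50 | 24% | 71% | 99% |
| 100 | 9% | 24% | 57% |

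That is the reason to rule out within-arm growth as evidence of benefit, including when the follow-up is interpreted.

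**4. Precision of the added comparison.** The plan gives no figure for the follow-up. Section 6.1 asks for 24 completers from 30 recruited; 1:1 allocation is assumed here. The 95% half-width for a difference in means, in SD units, is t × √(2/n):

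- n = 12 per arm: 2.074 × √(2/12) = 2.074 × 0.408 = 0.85
- n = 15 per arm: 2.048 × √(2/15) = 2.048 × 0.365 = 0.75

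Adjusting for a baseline measure with correlation r multiplies the half-width by √(1 − r²). With 12 per arm and t = 2.080 on 21 df, r = 0.5 gives 2.080 × 0.408 × 0.866 = 0.74, and r = 0.7 gives 2.080 × 0.408 × 0.714 = 0.61 (r assumed).

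Without adjustment, a two-sided 5% test with 80% power detects about 1.20 SD with 12 per arm and 1.06 SD with 15. Power for 0.5 SD is 22% and 26%. Loss between programme end and one year would lower these further.

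**The case against.** The strongest case on the other side is that the phrases in question are a loose statement of purpose, not an estimand or decision rule, and that Objectives B and C are already framed against specific word training. An active comparator is a legitimate design, and failing to separate both worked from neither worked after a null result is a general limit of such designs, not a mistake particular to this plan.

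Much of this stands. It does not cover the follow-up analysis, where the between-arm framing of Objective C is not carried through: the analysis text names the norm and nothing else.

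A reader might go further and infer that ordinary word growth over the nine weeks will itself be counted as benefit. The documents do not support that. Sections 3.3 and 6.3.2 judge programme-period vocabulary between randomised arms with baseline vocabulary in the model, and no within-arm growth test is planned. The 40 to 68 words are for typically developing infants and do not measure bias in any planned test.

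A reader might also infer that a null result would be reported as a short-lived benefit of both programmes. No section says so. Under section 3.3 a null result simply fails the success criterion. The wording of 6.3.2 leaves that reading open; it does not commit anyone to it.

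**Conclusion.** The concern holds for the one-year follow-up and only there. The aim in 6.3.2 is absolute, the design is relative, and the single named comparator can neither isolate the effect of a programme nor deliver Objective C. No planned test is biased by this, so its size is not a number of words. What is at issue is the type of conclusion that can be drawn at one year, and the absence of one promised analysis.

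The cancellation of shared influences between arms rests on randomisation and is weakened by loss to follow-up and by restricting analysis to children who complete the intervention (section 6.3). The precision figures rest on 1:1 allocation and on every completer being seen at one year.

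The change is worth making before the follow-up data are analysed, because it alters what the trial can claim. It does not call the nine-week vocabulary analysis into question.

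**What to change.** In the follow-up paragraph of 6.3.2:

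- Replace the aim about the effects of each programme, and about benefit confined to the programme period, with whether the two randomised programmes differ at one year.
- Add a between-arm analysis of the follow-up language score and the WPPSI-IV scores, reported as an adjusted difference with a 95% interval. Adjust the cognitive scores for the initial WPPSI-IV result, and language for baseline checklist vocabulary, since the BPVS3 has no baseline. Section 4.3.2 places the initial WPPSI-IV at week 2, once training has begun; say so when calling it baseline.
- Keep the comparison with the UK standardised mean as descriptive only.
- State that growth within an arm, or in both arms together, will not be reported as programme benefit, because there is no untreated group.

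This needs no extra participants, visits or measurements. The cost is a narrower claim, and a between-arm estimate that will be imprecise at this sample size and should be presented as such. Keeping the absolute claim would need an untreated comparator. As an illustration, a third arm powered pairwise for 0.5 SD (two-sided 5%, 80% power, no multiplicity adjustment) takes 64 completers per arm, 3 × 64 = 192 in all, against the planned 24.

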3.1. Primary objectives

The main objectives of the present study are:

- A. To investigate whether it is possible to teach Late Talkers to attend to objects' shapes as a useful property for learning and generalizing novel object labels.
- B. To assess the benefits that this intervention programme has on Late Talkers' short-term vocabulary development compared to an intervention where infants will be taught specific words ('specific word' intervention).
- C. To assess the benefits of the intervention programme on language and cognitive development one year after the intervention compared to the 'specific word' intervention.

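### One-year outcomes are compared only with UK norms, so the main objective of shape training versus specific-word training at one year (Objective C) is never tested

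*Combined protocol and SAP*

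**What the plan says.** Section 3.1 states Objective C, one of three main objectives, as "To assess the benefits of the intervention programme on language and cognitive development one year after the intervention compared to the" specific-word intervention. Section 4.2 provides the design for that comparison: "Infants will be randomly allocated to one of two groups".

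Section 6.3.2 describes the follow-up analysis. Its aim is to see "if there are any long-term effects of each intervention". On cognition it says "The cognitive assessments will be used to assess whether the intervention has an effect on visual spatial skills and working memory", and gives the method as "In both cases, it will be done by comparing the infants results to the standardized mean of UK infant population". On language, the child's "result in the follow up language assessment will be compared to the standarized mean of UK infant population".

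Intervention type does enter a model in 6.3.2, but the outcomes of that model are fixed: "The factors that predict the number of noun extensions based on shape as well as vocabulary growth will be assessed using mixed effect model analyses". Vocabulary growth comes from the parent checklist, and section 4.3.1 sets its timing: "In the first and last session, parents/guardians will also be asked to fill in the UK-CDI Words and Gestures questionnaire". Section 4.4 lists only BPVS3 and WPPSI-IV at one year. Section 6.3.3 adds attention and sorting as factors and no follow-up contrast.

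**The concern.** The objective names one comparator and the analysis uses another. Whether a child group lies above, at or below a national mean is a different question from whether one training did better than the other.

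Distance from the norm one year on mixes any training effect with where the children started, ordinary maturation and spontaneous catch-up, which section 1.2 says some Late Talkers show. For children with severe delay it also includes the NHS programme they may have begun by then; section 4.1.3 puts that wait at up to a year. Randomisation balances these influences between arms on average, but only a comparison between arms benefits from it.

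At stake is one of the three main objectives. If the plan is followed to the letter, Objective C has no answer, and 6.3.2 invites the reader to treat a norm comparison as evidence that the intervention worked or failed. Objectives A and B are not affected by this point.

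**Working it through.** **Reading the text.** The point rests on the wording, not on arithmetic.

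| Item | Objective C (3.1) | Follow-up analysis (6.3.2) |
|---|---|---|
| Time | one year | one year |
| Domains | language, cognition | language, cognition |
| Comparator | specific-word arm | UK standardised mean |
| Between-arm term | required | none stated |

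The phrase about effects of each intervention suggests results by arm, so the natural reading is two separate norm comparisons. Two comparisons with a constant are still not a comparison with each other.

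**The plan's own figure.** Section 6.1 gives 24 finishers for power 0.8, a medium effect and error probability 0.05, but names no test, so 24 cannot be reproduced. It is used below only as a head count. A two-sided two-sample t-test at d = 0.5 would need 64 per arm.

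**Illustration: what separate norm comparisons can show when the arms are identical.** Assumptions: 12 per arm (an equal split of 24), or 15 per arm (an equal split of the 30 to be recruited); two-sided 5% one-sample t-tests, since 6.3.2 names no test; SD equal to the norm SD; both arms at the same true gap δ from the norm.

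- Power of one arm: p = P(|T| > t(0.975, n−1)), where T is noncentral t with parameter δ√n.
- For n = 12, δ = 0.5: 0.5 × √12 = 1.732, so p = 0.353.
- Chance that exactly one arm is significant: 2p(1−p) = 2 × 0.353 × 0.647 = 0.457.
- For n = 15, δ = 0.5: p = 0.438, and 2 × 0.438 × 0.562 = 0.492.

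| Gap δ (SD), n = 12 | p | 2p(1−p) |
|---|---|---|
| 0 | 0.050 | 0.095 |
| 0.2 | 0.097 | 0.176 |
| 0.5 | 0.353 | 0.457 |
| 0.62 | 0.500 | 0.500 |
| 1.0 | 0.883 | 0.207 |
| 1.3 | 0.983 | 0.033 |

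With 15 per arm the maximum, 0.500, is at 0.54 SD, and the figure falls to 0.007 at 1.3 SD.

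**What the between-arm comparison would deliver.** Assumptions: two-sided 5%, d = 0.5 for the medium effect of 6.1. The noncentrality parameter is d√(n/2) and the CI half-width is t(0.975, 2n−2) × √(2/n).

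- n = 12: 0.5 × √6 = 1.225, power 0.216; half-width 2.074 × √(2/12) = 0.85 SD; difference detectable with 80% power 1.20 SD.
- n = 15: 0.5 × √7.5 = 1.369, power 0.262; half-width 2.048 × √(2/15) = 0.75 SD; detectable difference 1.06 SD.
- With fewer children returning: power 0.185 (half-width 0.94 SD) at 10 per arm, and 0.154 (1.07 SD) at 8 per arm.

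Baseline adjustment was simulated (20,000 runs, 12 per arm, assumed baseline–outcome correlation r). One covariate gives power of about 0.21 at r = 0, 0.27 at r = 0.5 and 0.36 at r = 0.7. Adding a second, uninformative covariate gives about 0.20, 0.26 and 0.34. With 15 per arm and two covariates, power is about 0.31 (r = 0.5) and 0.43 (r = 0.7).

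**The case against.** The best defence is that a between-arm comparison is implied: 6.3.2 speaks of each intervention, and intervention type already appears in its models. This does not succeed. The models' outcomes are named and exclude the one-year tests. For Objective B the section says outright that the analysis will show whether shape training gave more growth than the control. For Objective C it states a different comparator. That is a stated rule, not an omitted detail.

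Several narrower objections have force:

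- The 46% figure is near its maximum and assumes that each arm is tested against the norm and the two verdicts are then compared, which the plan does not say. Other gaps are plausible. Children with cognitive delay are screened out, which points to a small cognitive gap (about 10% at zero, 18% at 0.2 SD). The 15th-percentile description in section 1.2 concerns expressive vocabulary; as a rough guide it implies about 1.04 SD or more, and so 17% or less with 12 per arm. The figure is illustrative only.
- The comparison would not be fully protected by randomisation. Sections 6.3 and 6.3.2 analyse only children who complete the intervention, and section 4.1.4 requires a separate signature for follow-up contact.
- Section 3.3 promises expressive as well as receptive language at one year, but the language test in 4.4 is receptive. A between-arm analysis cannot fill that gap, which is a separate defect.
- Power is low whatever is done. This limits what Objective C can conclude, but it does not make the norm comparison an answer to it. An imprecise estimate of the right difference still addresses the objective.

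**Conclusion.** The concern holds and should be corrected before analysis. As written, 6.3.2 leaves Objective C unanswered and uses a norm comparison to judge whether the intervention has an effect, which that comparison cannot show. This follows from the text alone. The calculations indicate only scale: with identical arms, separate norm comparisons would give conflicting verdicts in about 3% to 50% of trials for gaps between 0 and 1.3 SD (12 per arm). These figures assume t-tests, the norm SD and equal arms. With the correction, Objective C can be analysed but is unlikely to be settled: unadjusted power at d = 0.5 is 22% to 26%, with a 95% CI of about ±0.85 to ±0.75 SD, for 12 to 15 per arm.

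**What to change.** Replace the follow-up paragraph of 6.3.2 with wording such as:

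> Objective C will be analysed by randomised group. Each one-year score (BPVS3, WPPSI-IV visual spatial, WPPSI-IV working memory) will be regressed on intervention type. Cognitive outcomes will be adjusted for the corresponding initial WPPSI-IV score; BPVS3 will be adjusted for the session-1 UK-CDI count of words understood and for age. The between-arm difference and its 95% CI will be reported for all three outcomes, as estimation. Comparison with UK norms describes whether children are catching up and will not be used as evidence of an intervention effect.

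Words understood is the matching baseline because BPVS3 is receptive and 6.3.1 records two counts. Age is needed because the count is raw and entry spans 24 to 48 months. State whether raw or standardised follow-up scores are used.

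Add these limits:

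- With 12 to 15 per arm, or fewer, a non-significant difference is not evidence of no long-term effect.
- Report the numbers randomised, completing and returning in each arm, because the comparison is among children who complete and return.
- As 4.3.3 is worded, training runs through the first seven weeks, so the week-2 WPPSI-IV follows the first training session. Check this against Figure 1 and say so.
- The three outcomes do not cover expressive language; reconcile 3.3 with 4.4 separately.

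The cost is SAP wording and three regressions. The tests and baselines are already scheduled, so no new data are needed. The drawback is low power: with 12 per arm at d = 0.5, about 27% to 36% with one covariate and 26% to 34% with two if the baseline correlation is 0.5 to 0.7 (an assumption), and about 20% to 21% if the covariates carry no information.
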